EQ-5D-5L will be used to measure quality of life of YAs and caregivers. EQ-5D-5L is a widely used, patient-reported outcome measure that assesses health-related quality of life across five dimensions: mobility, self-care, usual activities, pain/discomfort, and anxiety/depression. Users answer a short questionnaire by selecting the level of difficulty they experience in each dimension and also rate their overall health on a visual analogue scale. This information is used to inform healthcare decisions, compare health states, and track changes in health over time. The EQ-5D-5L shows good convergent validity, meaning it correlates well with other established health status measures like the SF-36, SF-6D, and the WHO-5 Well-Being Questionnaire. Cronbach's alpha for the EQ-5D-5L has been reported as excellent (e.g., 0.79) (Dams et al., 2021).

The UCLA 3-Item Loneliness Scale will be used to measure the social connectedness levels of YAs and caregivers. This brief instrument has been widely used in public health and psychosocial intervention studies, is validated across multiple European languages, and effectively captures perceived social connectedness in pre- and post-intervention assessments. shows good reliability and validity, particularly with high internal consistency and temporal stability. Its reliability is supported by Cronbach's alpha values 0.81-0.89, and test-retest reliability is good, with correlations around 0.71. For validity, this tool demonstrates concurrent validity through significant correlations with other loneliness measures (Alsubheen et al., 2023; Katsiroumpa et al., 2025).

The Brief Fatigue Inventory (BFI) will be used to measure YAs' physical activity patterns. The Brief Fatigue Inventory (BFI) is a short, self-administered questionnaire used to measure the severity of fatigue and its impact on daily life in cancer patients (MDAnderson Cancer Center, 2025). It consists of nine items; each rated on a 0–10 scale and is designed to be completed in under five minutes. The tool assesses both the patient's current level of fatigue and how much it has interfered with various activities over the past 24 hours, such as general activity, mood, walking, work, and relationships. The BFI has shown adequate values of internal consistency (α Cronbach = 0.94), substantial reliability [ICC_{2,1} (95% CI) = 0.87 (0.81 to 0.91)] and very good agreement (standard error of measurement = 1% and MDC90% = -0.37) (Nunes et al., 2019).

Since the selected outcome measurement instruments (e.g., WEMWBS, EQ-5D-5L, GSE, BFI) are validated self-report measures suitable for use in adult populations, they will be self-administered. Local staff will be available to assist participants with any technical issues or clarifications during online questionnaire completion, while the participant responses should remain independent.

In order to address the potential lack of change in the outcome measures and to capture the qualitative aspects of participants' experiences, we will incorporate open-ended questions to the data collection materials. These questions will focus on participants' perceptions of the

intervention's effectiveness and its components, assessing their usefulness or lack thereof. This approach will provide valuable insights alongside the quantitative data.

Assignment methods and blinding

Participants will be assigned individually to the intervention. No restrictions, such as blocking, stratification, minimisation, are planned regarding the assignment of units to study condition, i.e., YAs with cancer diagnosis. There will be no randomisation or matching of participants, and all eligible participants will be assigned to the intervention.

Data analysis

Unit of analysis will be based on assessing the impact of the intervention at the individual level. Statistical methods will be employed to provide a descriptive analysis of the baseline and follow-up data. If permitted by the data, regression analyses will be performed. Subgroup analyses and adjusted analyses will be performed as needed. Intention to treat (ITT) principle will be followed for inputting missing data for the two pre- and post-intervention data collection points, using their last available data (Sainani, 2010). The characteristics of the data of the participants who did not take part_in the post-intervention data collection will be analysed and presented. IBM SPSS 27 statistical analysis package programme will be used for data analysis.

Ethics

Ethics approvals will be obtained from the local research ethics committees in the participating six countries. All participants will be required to give informed consent before participating in the study. They will be provided with the study materials in advance before making any decisions regarding participation. They will have time to think about their participation for at least seven days. The participants will have the right to withdraw from the study without giving any reason and this will not lead to any consequences.

Data management plan

Principles of data collection: Personal data (age, gender, health-related data, address, phone number) will be collected locally in a way that limits the negative impact on the participants. The participants' addresses will be collected to identify suitable local green and blue spaces where the walks will take place. Microsoft Forms will be configured to ensure that responses are not associated with participants' email addresses. People with cancer and caregivers can be seen as a vulnerable patient group due to the severe health situation and thus, require a sensitive approach and the ability to emphatically recognise the situation at hand. Extra psychological harm must not be delivered to them, nor to their close family members. Data will be collected in a way that ensures fairness, transparency, and accountability of the data processing, data quality, and confidentiality. Personal data will be collected, analysed, stored, and shared in full compliance with European (i.e., GDPR

2016 requirements) and national legislation, conventions, declarations, and manuals relevant to the country of the data collection taking place. Data collection will be based on informed consent from the participants. Data collected will be used only for the purposes of the current project. No data that is not strictly necessary to complete the current study will be collected. All partners will be asked to work with their local Data Protection contact person responsible for overseeing all personal data processes on that research site.

Processing and storing of data: There will be two types of data for processing and storing. The pre-post online questionnaires (including the outcome measures, e.g., Distress
Thermometer, etc.) will be collected anonymously using unique identifiers via Microsoft Forms and stored and processed in Ireland at University of Galway. The pre-post intervention questionnaire data will be stored in multi-factor authenticator password-protected
SharePoint folders in the Irish study site, University of Galway. The project partner teams will be given access to their collated anonymous data for translation into English from their local languages so that the University of Galway team can perform the data analysis for the whole data collected from six countries. The consent forms to take part in the intervention and key/code list with participant personal and contact details will be obtained and stored locally by each partner country. No individual participants will be identifiable in the reports produced from the study. Ultimately, all non-personal data will be freely available as an open anonymised resource for further research.

Data storage and security: The consent forms to take part in the intervention and key/code list with participant details will be obtained and stored locally by each partner country in password-protected SharePoint folders. The pre-post questionnaire data will be stored in multi-factor authenticator password-protected SharePoint folders in the Irish study site, University of Galway. After data processing, partners will have access to their collated anonymous data for translation purposes, and they will be required to comply with EU and national data protection legislation and best practices for data security. University of Galway institutional policies will be followed for data storage, protection, retention, and destruction, in line with GDPR 2016 regulation. In line with the University of Galway data retention policy, the data will be retained securely for 7 years via multi-factor authenticator password-protected SharePoint folders of the Irish project team members. Details of local arrangements for protection will be supplied by each partner based on their institutional policies. Details of such arrangements will be presented by each partner when applying for ethical approval to the local ethics committee.

Confidentiality and privacy: When applying for ethical approval, partners will be required to supply detailed information on how privacy and confidentiality will be ensured for participants' data. Before consent is obtained from participants and before the data collection starts, project personnel must inform participants of the purpose for which personal information provided will be used, any potential risks related to confidentiality or anonymity

of personal data, which individuals will have access to personal data, and under what circumstances such access will be granted.

Risks to participants

Although minimal, there is a risk of injury, discomfort or distress during the walks in green and blue spaces and online physical exercises. The participants will self-declare their fitness. Prior to the intervention, the PAR-Q, Physical Activity Readiness Questionnaire, will be used as a screening tool for physical activity eligibility assessment and presence of any contraindications, and if any issues are found, the participants will be advised to seek advice from a doctor. The exercise sessions will be developed by qualified physiotherapists or exercise physiologists who are trained to develop exercise programmes for cancer patients. Group walk facilitators will be provided by 'MELODIC WP4 - Guidelines for Group Walk Facilitators' (Appendix) to assist them with preparation and facilitation of the group walks safely. For example, a risk assessment using a standard tool will be conducted (e.g., Unit Risk Assessment Methodology https://www.universityofgalway.ie/media/healthsafety/Part-3--- Unit-Risk-Assessment-Methodology-2022.pdf). In case some of the participants experience growing anxiety or distress during the group walks or the interactive lessons, HCPs can guide them to get professional help to manage distress. In addition, there will be a distress protocol in place to be used by the facilitators (if needed) during the group walks and interactive lessons.

Incentives

To support participants and increase compliance with the intervention activities, minor incentives such as refreshments, items with the MELODIC project logo (e.g., T-shirts), where applicable, entrance tickets to a national park or botanical garden, etc., will be budgeted and provided locally.

Benefits of the study

The expected benefits to YAs with a lived cancer experience and caregivers will include improved mental health, specifically a reduction in symptoms of psychological distress, which may lead to enhanced general wellbeing and quality of life. The social benefits may include increased social connectedness and peer support and reduced social isolation. Additionally, by taking part in the intervention, the participants may improve their physical activity patterns, and their fatigue levels may be reduced.

4. References

All Ireland Social Prescribing Network (2025). Social Prescribing for Children and Young People: A Growing Opportunity to Enhance Well-Being. Available at:

https://www.allirelandsocialprescribing.ie/post/social-prescribing-for-children-and-young-people-a-

growing-opportunity-to-enhance-well-being#:~:text=Research%20Highlights,networks%20and%20meaningful%20engagement%E2%80%8B.

Alsubheen, S. A., Oliveira, A., Habash, R., Goldstein, R., & Brooks, D. (2023). Systematic review of psychometric properties and cross-cultural adaptation of the University of California and Los Angeles loneliness scale in adults. *Current Psychology*, 42(14), 11819-11833.

Barr, R. D., Ferrari, A., Ries, L., Whelan, J., & Bleyer, W. A. (2016). Cancer in adolescents and young adults: a narrative review of the current status and a view of the future. *JAMA pediatrics*, 170(5), 495-501.

Barsevick, A. M., Sweeney, C., Haney, E., & Chung, E. (2002). A systematic qualitative analysis of psychoeducational interventions for depression in patients with cancer. Database of Abstracts of Reviews of Effects (DARE): Quality-Assessed Reviews [Internet].

Bikomeye, J. C., Balza, J. S., Kwarteng, J. L., Beyer, A. M., & Beyer, K. M. (2022). The impact of greenspace or nature-based interventions on cardiovascular health or cancer-related outcomes: A systematic review of experimental studies. *PLoS One*, 17(11), e0276517.

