The intervention is designed to provide a comprehensive approach that addresses the physical, psychological, and social dimensions of well-being of YAs with a lived cancer experience and caregivers. By employing a multidisciplinary strategy, the programme draws on the expertise of various professionals, including mental health specialists, exercise physiologists, and other healthcare professionals, to deliver a well-rounded experience. Central to this intervention is the integration of psychoeducation with structured physical activity components. The psychoeducation component focuses on educating participants about their diagnosis, treatments, mental health concepts, coping strategies, the importance of emotional resilience, and the benefits of physical activity. This knowledge will support participants to understand their mental health better and to use effective tools for managing stress and emotional challenges. The structured physical activity components – guided group walks in natural surroundings and online physical exercises – aim to support patients and caregivers peer-support and social networks and encourage participants to engage in regular exercise, promoting not only physical fitness, but also enhancing mood and reducing symptoms of anxiety and depression. These activities are designed to be inclusive and adaptable to varying fitness levels, ensuring that everyone can participate. Inspired by the concept of social prescribing, this intervention also connects participants with support groups and social activities, fostering a sense of belonging and community engagement. This holistic approach aims to cultivate a supportive environment for YAs with a lived cancer experience and caregivers, ultimately improving their overall quality of life. The goal is to empower participants not only through psychoeducation and physical activity but also by strengthening their social networks and support systems.

A summary of the intervention is provided in Figure 2. The implementation of the intervention study will take nine months, excluding holidays. It will consist of three phases: three months for baseline data collection, three months for delivering the intervention, and three months for collecting post-intervention data. A diagram of the intervention study phases and components will be provided to participants to help them organise their time and participate regularly in the intervention (Figure 3).

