	Intervention components	\circ	Effect and outcome measurement
	Interactive psychoeducation	O	instruments
N	session 1	U	Pre-test: Month 0 (baseline)
	At baseline	J	Post-test: Month 3 (immediately
Т	Duration: 90 minutes	Т	post-intervention)
•		•	Primary outcome measurement
E	Guided group walks with YAs and their family members/caregivers	C	(mental health):
	once a week for 12 weeks for each		For YAs and caregivers: Warwick-
R	group, alternating green and blue	0	Edinburgh Mental Health Wellbeing
	spaces. HCPs will guide the walks.		Scale; The Distress Thermometer.
V	Duration up to 1 hour.	M	Secondary outcome measurement
·	Online exercises	, -	(general wellbeing and quality of
E	30-minute resistance exercises twice	E	life):
	a week for 12 weeks (recording will		For YAs and caregivers:
N	be provided to participants at the	S	EQ-5D-5L (improved health-related
- `	beginning of the intervention) - total		quality of life);
Т	3 videos with different workouts.		Social connectedness - UCLA 3-Item
-			Loneliness Scale; qualitative
	Internative nevel podvention		questions in pre- and post-tests.
-	Interactive psychoeducation session 2		For YAs:
0			
	At 1.5 months		Coping abilities - General Self-
N	Duration: 90 minutes		efficacy Scale (cancer-specific).
			Physical activity - Brief Fatigue
	Interactive psychoeducation		Inventory (BFI); quantitative and
	session 3		qualitative questions in pre- and
			post-tests on the patterns of physical
	At 3 months		activity.
	Duration: 90 minutes		Post-test on study feasibility:
			Questionnaire completed by HCPs,
			YAs, and caregivers about the study's feasibility.
			siday a reasibility.

Figure 2. Summary of the intervention and targeted outcomes

Social prescribing-inspired physical activity in natural surroundings

Guided group walks

Local healthcare professionals (HCPs) will organise and facilitate group walks in green and blue spaces. Green and blue spaces are natural or semi-natural environments that include vegetated areas (green spaces) and bodies of water (blue spaces), such as parks, forests, lakes, rivers, canals, and coasts. Guided group walks will alternate between green and blue spaces, taking place in a green space every other week and a blue space on the alternate weeks. Each walk will be scheduled for 1 hour, which will include a warm-up and breaks as needed. The total duration of each individual's walking time during the hour will depend on the fitness levels of the participants.

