Guided group walks will be organised once a week for 12 weeks (3 months) for each intervention group. Group compositions will be decided on a local level and in line with participants' preferences, with the following group compositions being possible: (1) YA and caregivers groups meet separately and at different times; (2) YA and caregiver groups meeting separately but at the same time; (3) mixed groups of YA and caregivers. This flexible approach aims to ensure that participants feel comfortable and supported during the walks.

The psychoeducation and information support component will consist of three online group interactive sessions for YAs and caregivers facilitated by trained health care professionals at baseline, 1.5 months, and 3 months following the start of the intervention. If preferred and depending on local circumstances, in-person sessions can also be conducted. The interactive sessions will last approximately 90 minutes, and each will follow a pre-planned schedule that allows for discussion. Topics will include information and discussion around the topic of living with cancer, treatments, and life after cancer treatments, and discussion among the participants will be encouraged. In addition, time will be allocated to address participants' special interests and needs, which will be discussed with them prior to the sessions.

In the first interactive session, the participants will be introduced to each other and will get to know each other with the aim of encouraging them to form relationships, gain and provide peer support, and reduce social isolation. General information about psychosocial support and psychoeducation, as well as the intervention's objectives and components, will be presented. In addition, information about the online exercise sessions, the benefits of exercise, recommended dose, and types of exercises beneficial for YAs living with cancer will be introduced. The second interactive session will focus on topics for further development and discussion as identified by participants in the first session, and informed by the findings from WP2 needs assessment, such as mental and emotional challenges of a cancer diagnosis and how these might be addressed. The last session will be a summary of topics and a

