discussion on the long-term impact of cancer, information on survivorship and life after cancer, including return to work/studies, how to manage adverse effects of treatments, mood changes, sleeping, nutrition, relationships, sexuality, work, career, and education, starting a family, and financial support. The same HCP who facilitated the sessions will participate in the walks with the groups and will be available for further informational support. If some participants experience growing anxiety or distress due to the topics covered in the sessions, HCPs will guide them towards professional help for managing their distress.

Online physical exercises

Online 30-minute resistance exercise sessions will be held with young adults twice a week for 12 weeks. Caregivers may choose to participate in the exercises if they wish. Participants will receive recorded sessions at the beginning of the programme and will have the option to either join live group exercise sessions at a designated day and time or perform the exercises at their convenience by watching pre-recorded videos. Participants will be encouraged to repeat the exercises at home using these videos at least one more time each week. They will be asked to record the number and duration of exercise sessions they completed.

Follow-up discussions will be held during weekly walks or interactive sessions to address any challenges participants encounter while exercising and to promote consistent participation. A physiotherapist or exercise physiologist will design exercises specifically for cancer patients and create three pre-recorded videos, each featuring a different workout routine targeting specific muscle groups along with recommendations around the number of repetitions and how to increase these over time.

1	STUDY PHASES													
STUDY COMPONENTS	Pre- intervention data collection	ntion 12 weeks											Post- intervention data collection	
	12 weeks	1	2	3	4	5	6	7	8	9	10	11	12	12 weeks
Pre-intervention questionnaire														
Guided group walks														
Online exercises x 2 /week		T		П	П									
Interactive psychoeducation sessions														
Post-intervention questionnaire														

Figure 3. Diagram of the MELODIC intervention components and schedule

Tailoring of the intervention.

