The MS Forms will be used for the study's online data collection platform, to be uniform across all partners' data. Quantitative and qualitative questionnaires and previously developed and validated instruments (detailed below) will be used for data collection. Translations, language adaptations, and validity and reliability assessments of these instruments will be performed by the project partners if the instruments are not readily available in their local language.

Data will be collected at two time points: baseline and immediately post intervention using the MS Forms platform and will be stored on a two-factor authentication SharePoint. The Irish partner (University of Galway) will create links for the local partners, who will complete any language adaptions or translations. The local partners will distribute the link in their national language to their local participants, who will have been provided with a unique identifier number that both the young adults with a lived experience of cancer and their caregivers will include on the forms. Participants' anonymous responses will be returned via MS Forms to the Irish partner only, and the Irish partner will give access to the collated anonymous data to the partners so that they can translate the responses to English for analysis by the University of Galway, who will conduct the analysis for all partners. This will allow for

uniformity across the partners, while also supporting cultural/language nuances to be maintained to the greatest extent. A range of quantitative and qualitative questionnaires and previously developed and validated instruments (detailed below) will be used for data collection.

Warwick-Edinburgh Mental Health Wellbeing Scale (WEMWBS) will be used to measure the mental health status of YAs and caregivers. The WEMWBS is a 14-item scale of positively worded statements covering feeling and functioning aspects of mental well-being (Tennant et al., 2007). WEMWBS demonstrates good validity and reliability across diverse populations, as supported by studies showing strong internal consistency (Cronbach's alpha < 0.89), high test-retest reliability (0.83), and a single-factor structure confirmed by factor analysis (Stewart-Brown et al., 2011). The scale accurately reflects population groups, responds to change in various interventions and patient populations, and has a valid and reliable short version, the SWEMWBS, for populations where a shorter measure is needed (CORC, 2025).

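### Questionnaire timing is stated in two ways: fixed points at Month 0 and Month 3, and 12-week collection phases that permit a pre-post interval of 12 to 36 weeks

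*Protocol*

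**What the plan says.** The protocol describes assessment timing in four places, all under 3. Methods.

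- Figure 2 gives fixed points: "Pre-test: Month 0 (baseline") and "Post-test: Month 3 (immediately" after the intervention).
- The data-collection text that follows Study feasibility agrees: "Data will be collected at two time points: baseline and immediately post intervention".
- The Intervention section describes consecutive phases: "three months for baseline data collection, three months for delivering the intervention, and three months for collecting post-intervention data". It introduces them with "The implementation of the intervention study will take nine months, excluding holidays".
- Figure 3 has a column headed "Pre- intervention data collection" marked as 12 weeks, then weeks 1 to 12 of the programme, then a post-intervention collection column also marked as 12 weeks. The Intervention section says this diagram goes to participants so that they can plan their time.

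The programme itself is tied to each group: "Guided group walks will be organised once a week for 12 weeks (3 months) for each intervention group". The psychoeducation sessions fall "at baseline, 1.5 months, and 3 months following the start of the intervention". No section says how close to a group's first or last session a participant must answer. The Data analysis section does not mention the time between the two assessments.

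**The concern.** The two descriptions do not define the same measurement. A post-test completed ten weeks after the last walk complies with the Intervention section and Figure 3, but not with Figure 2 or the data-collection text. A baseline completed ten weeks before week 1 raises the same problem at the other end.

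The design makes this matter. Under Assignment methods and blinding, every eligible participant receives the intervention, so pre-post change is the only measure of effect for Hypothesis 2. Participants are within 24 months of diagnosis, a period in which mental wellbeing and distress may change on their own. With no comparator, change between an early baseline and the start of the programme cannot be separated from the programme's effect. A late post-test measures how far an effect has lasted, not its level at the end.

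The Data analysis section also fills missing values with the last available data. With two time points, a baseline taken well before the start could stand in for a missing post-test.

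An analysis plan written later can define windows, but it cannot recover an end-of-programme measurement that was never taken at the end of the programme.

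**Working it through.** **Inputs**

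| Quantity | Value | Source |
|---|---|---|
| Baseline collection phase, B | 3 months; 12 weeks | Intervention; Figure 3 |
| Delivery phase, D | 3 months; 12 weeks | Intervention; Figure 3 |
| Post-intervention collection phase, P | 3 months; 12 weeks | Intervention; Figure 3 |
| Programme length per group, L | 12 weeks, equated with 3 months | Guided group walks |
| Nominal pre-test and post-test | Month 0 and Month 3 | Figure 2 |

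**1. The plan's own total.** B + D + P = 3 + 3 + 3 = 9 months, which agrees with the stated duration. In Figure 3's units, 12 + 12 + 12 = 36 weeks.

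**2. Shortest interval.** Baseline on the last day of its phase and post-test on the first day of its phase: 0 + D + 0 = 12 weeks. This matches the nominal Month 0 to Month 3.

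**3. Longest interval.** Baseline on the first day of its phase and post-test on the last day of its phase: B + D + P = 12 + 12 + 12 = 36 weeks, or 36 / 12 = 3 times the nominal interval. At this bound the baseline is 12 weeks old at the start and the post-test comes 12 weeks after the end.

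**4. Sensitivity to the unit.** With calendar months, three months is about 52 / 4 = 13 weeks, and the range becomes about 13 to 39 weeks. Holidays are excluded from the nine months and could lengthen it further.

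**5. Could staggered group starts explain the long phases?** Room for staggering inside the delivery phase is D − L = 12 − 12 = 0 weeks. If the phases run in sequence as stated, all groups start together, so the collection phases are not accounted for by groups starting at different times.

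**6. Effect of a per-group window.** If the pre-test is allowed a weeks before the start and the post-test b weeks after the end, the interval runs from 12 to 12 + a + b weeks. The values of a and b below are illustrations; the protocol gives none.

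| a | b | Range (weeks) |
|---|---|---|
| 1 | 1 | 12 to 14 |
| 2 | 2 | 12 to 16 |
| 2 | 4 | 12 to 18 |
| As written: 12 | 12 | 12 to 36 |

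Only the column headings of Figure 3 are used here. The marks inside its rows were not legible in the text available, and nothing above depends on them.

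**The case against.** The best defence is that the three phases are a fieldwork calendar for a six-country study, while Figure 2 and the data-collection text govern the individual participant. The sentence about phases does describe how long the study takes to implement, and Figure 2 and the data-collection text agree with each other. This may well be what was intended. But the protocol does not say so, the delivery phase leaves no slack for staggering, and the phase diagram is handed to participants as a planning aid. The defence lowers the severity; it does not remove the conflict.

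Four stronger readings are tempting, and the documents do not support them.

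- *The typical interval will be 24 weeks, double the nominal one.* That figure (6 + 12 + 6) requires completion spread evenly over both phases. Nothing in the protocol suggests this pattern, and it runs against the stated intention to measure directly after the programme.
- *The mean change will be biased because timing differs by country or by distress.* This is plausible, but the protocol gives no basis for its size or direction. The 24-hour reference period is documented for the Brief Fatigue Inventory, a secondary outcome, and no recall period is given for the Distress Thermometer.
- *Pre-tests may follow session 1, or post-tests may precede session 3.* The 36-week bound requires the phases to run in sequence, and in that case neither can happen. What remains is a secondary ambiguity: sessions and tests share the nominal times of baseline and 3 months.
- *Only in-window questionnaires should enter the primary analysis.* That would drop observed participants, contrary to the intention-to-treat statement under Data analysis.

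**Conclusion.** The concern holds as an internal conflict. Figure 2 and the data-collection text fix two time points; the Intervention section and Figure 3 allow 12 weeks of collection on either side of the programme; and no participant-level window links them. The text permits a pre-post interval of 12 to 36 weeks. This rests on reading the phases as consecutive and as available to any participant, which is how they are written. The 36 weeks needs the earliest possible baseline and the latest possible post-test in the same person.

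The consequence is that the primary change scores could combine effects at different times with pre-programme drift. How much this would shift the result cannot be computed, because the protocol gives no rate of natural change and no expected pattern of completion.

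This is a feasibility study of preliminary effectiveness, and a few sentences resolve the conflict. It should be fixed before the questionnaire links open, since late post-tests and old baselines cannot be repaired afterwards.

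**What to change.** Reconcile the Intervention section, Figure 2, Figure 3 and the data-collection text by tying each questionnaire to the group's own schedule.

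- **Pre-test:** completed shortly before, and always before, the group's first psychoeducation session.
- **Post-test:** opened after the later of session 3 or week 12, and closed after a short stated window. Fourteen days is an illustrative choice. The same length at the pre-test would give a range of 12 to 16 weeks.
- **Phases:** limit the two 12-week collection phases to recruitment, reminders and data handling. If group starts are to be staggered, restate the delivery phase so that it allows for this.
- **Records and analysis:** record the completion date of every questionnaire alongside the group's first and last session dates. Keep all observed data in the primary analysis, in line with the intention-to-treat statement, and use in-window data as a sensitivity analysis.

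The ordering rule also settles the shared baseline and 3-month labels for sessions and tests.

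The cost is protocol wording, a revised diagram for participants, and open and close dates on the forms. A shorter response window may lose some late responses. If starts are staggered, the delivery phase and overall calendar must be rewritten as well.
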